# **10. PUFF TOPOGRAPHY**

On Days 1 through 5, puff topography measurements will be performed for a 2 hour period during the last 2 hours of the 4-hour *ad libitum* product use session.

The following per-puff topography parameters will be recorded using Sodim Smoking Puff Analyzer Mobile (SPA-M) devices:

- Puff count
- Puff duration
- Puff volume
- Peak puff flow rate

- Average puff flow rate
- Inter-puff interval

The following per-product topography parameters will then be derived:

- Total number of puffs
- Total puff duration
- Average puff duration
- Total puff volume
- Average puff volume
- Average peak flow rate
- Average flow rate
- Total inter-puff interval
- Average inter-puff interval

Topography parameters will be listed by subject and per-product parameters will be summarised by study product, overall and by sex using descriptive statistics (n, mean, SD, CV%, SEM, minimum, Q1, median, Q3, maximum, and 95% CI).

A linear mixed model for ANOVA will be performed on the per-product topography parameters (no data transformation). The model will include sequence, product, and study period as fixed effects and subject-nested-within-sequence as a random effect. Sequence will be tested using subject-nested-within-sequence as the error term for informational purposes. LSMs and 95% CIs will be provided for the parameters by study product. LSM differences, 95% CIs of LSM differences, and p-values will be provided for the study product comparisons in per-product topography parameters. The same comparisons from PK analysis detailed above will be used.

The ANOVA analysis will be performed using the same SAS® code as outlined in the Statistical Analysis of Pharmacokinetic Parameters section above.

# **11. PRODUCT USE BEHAVIOUR**

On Days 1 through 5, subjects will use their randomised product (same product as the morning session) *ad libitum* for 4 hours starting after the 4-hour PK blood draw.

The number of cigarettes smoked, will be documented from Check-in until beginning of smoking abstinence (Day -1, until at least 12 hours prior to the start of morning controlled

product use on Day 1; Days 1 through 5, 8 hours post morning controlled use session IP start until at least 12 hours prior to the start of morning controlled product use scheduled on the following day). The number of cigarettes smoked and the number of HTP/HHP sticks used will be documented during each 4-hour *ad libitum* product use session (Days 1 through 5). The number of inhalations and reasons for missed puffs will also be documented.

The number of HTP/HHP sticks used (*ad libitum* product use session), the number of OBCCs smoked (Days -1 through 5), and the number of puffs (morning controlled product use session) will be listed by subject and summarised by study product, product use session, using descriptive statistics.

Incidence of device malfunction(s) will also be tabulated.

## **12. SAFETY**

All relevant case report form (CRF) and clinical laboratory data will be listed by subject and chronologically by assessment time point. This will include rechecks, unscheduled, and early termination assessments.

Applicable continuous variables will be summarised using n, mean, SD, minimum, median, and maximum.

The level of precision will be presented as follows: minimum/maximum in the same precision as in the database, mean/median in one more precision level than minimum/maximum, SD in one more precision level than mean/median, and n will be presented as an integer. Percentages will be presented as an integer.

Where individual data points are missing because of dropouts or other reasons, the data will be summarised based on reduced denominators.

Baseline will be the result closest and prior to the first product use on Day 1 unless otherwise stated. Summaries for post-baseline time points will not include rechecks, unscheduled, or early termination measurements.

Tables summarising safety data by assessment time point will only include summaries for baseline and post-baseline time points.

#### 12.1 Subject Disposition

Subjects will be summarised by the number and percent of subjects enrolled, randomised, completed the study, and discontinued the study (with discontinuation reasons) by randomised product sequence and overall.

Individual product use status (i.e., which products were administered to each subject) will also be provided along with their study completion status and date of study completion or discontinuation. The number of subjects with product use for each study product (i.e. A, B, C, D, and E) will also be presented.

# **12.2** Protocol Deviations

Protocol deviations are captured by the clinical site and provided in the CSR in a similar format to that provided by the clinical site. Protocol deviations are not edited or processed in SAS®.

# 12.3 Demographics

Descriptive statistics will be calculated for continuous variables (age, body mass index, height, and weight) by randomised product sequence and overall. Age will be approximated by subtracting the year of birth from the year of informed consent. If year of informed consent – year of birth is one more than the protocol maximum age (65) then the age approximation will be year of informed consent – year of birth – 1. Descriptive statistics for body mass index, height, and weight will be calculated using screening measurements.

Frequency counts will be provided for categorical variables (sex, race, and ethnicity) for each randomised product sequence and overall.

# 12.4 Smoking History and Usual Brand Attributes

Smoking history and usual brand attributes will be summarised with descriptive statistics for continuous variables by randomised product sequence and overall. Frequency counts will be presented for categorical variables for each randomised product sequence and overall. The continuous variables will include number of cigarettes smoked per day, number of years of cigarettes smoked, and the categorical variables will include usual cigarette brand, brand style, cigarette length and flavour. Subjects that only enrolled in the product trial and dropped prior to randomisation will be summarised separately.

Number of years smoked is calculated as stop year (year portion of Stop Date) – start year (year portion of Start Date). Where stop date is missing (i.e. smoking is ongoing), stop year is equal year of informed consent.

# 12.5 Adverse Events

All AEs occurring during this clinical trial will be coded using the Medical Dictionary for Regulatory Activities (MedDRA®), Version 26.1.

All AEs captured in the database will be listed in a by-subject data listing including verbatim term, coded term, product, onset date/time, resolution date/time, frequency, severity, relationship to study product, and action; however, only product use-emergent AEs (PUEAEs) will be summarised.

PUEAE is defined as an AE that is starting or worsening at the time of or after the first study product use. Each PUEAE will be attributed to a product based on the onset date and time of

the AE compared to that of the respective product administration date and time. An AE that occurs between products will be considered product use-emergent to the last product administered prior to onset of the AE. AEs occurring prior to the first product use episode on Day 1 but after the product trial has started on Day -1 will be attributed to the product trial.

If the onset time of an AE is missing and the onset date is the same as a product use date, then the AE will be considered product use-emergent in the prior and current product. If the onset time of an AE is missing and the onset date does not fall on a product use date, then the AE will be considered product use-emergent for the last product administered. If the onset date of an AE is missing, then the AE will be considered product use-emergent and attributed to each product on the study, unless the onset date is known to have occurred within or between specific product use periods.

PUEAEs will be tabulated by System Organ Class (SOC) and Preferred Term. Summary tables will include the number of subjects reporting the PUEAE and as a percent of the number of subjects that used study product by product and overall. The number of PUEAEs will be tabulated in a similar manner. A table, which summarises the number of PUEAEs by Preferred Term, severity, and relationship to study product, will also be included.

Serious adverse events (SAEs), if present, will also be listed. Applicable narratives will be included in the CSR.

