| Puff Topography | | | | X | X | | |

- a: To be performed within 28 days prior to study procedures on Day -1.
- b: At Check-in, baseline study assessments, questionnaire training and Product Trial will be performed on Day -1.
- c: Subjects will start study product use and study assessments.
- d: A follow-up telephone call will be made by the CRU in an attempt to contact all subjects who used at least one study product (including subjects who terminate the study early) using their standard procedures approximately 7 days after the final product use to determine if any AE has occurred since the last study visit.

Study Products:

| Product Designation | Product Type | Study Product Name |
|---------------------|--------------|--|
| A | HTP | [REDACTED] |
| B | HTP | |
| C | HHP | |
| D | HHP | |
| E | Cigarette | Subject's own brand combustible cigarette (OBCC) |

HTP, heated tobacco product

HHP, heated herbal product

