4.3.5 Tobacco Use/Considerations

Except as allowed by the study, consumption of tobacco- or nicotine-containing products will not be permitted from Check-in through discharge. On Days -1 through 5, subjects will be allowed to smoke their OBCCs, *ad libitum*, after completion of study assessments and after the 4-hour *ad libitum* product use session but will abstain from use of any tobacco- or nicotine-containing products for at least 12 hours prior to the start of morning controlled product use session scheduled on the following day.

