6.4.3 Puff Topography

Puff topography will be evaluated over the last 2-hour period during the 4-hour *ad libitum* product use session on Days 1 through 5 as indicated in the Study Events Flow Chart ([Table 1](#)). Following the 4-hour PK blood collection and at the start of their meal, subjects will be allowed to use their assigned study product *ad libitum* for 4 hours. During the last 2 hours of the *ad libitum* session, topography measurements will be taken. The SPA-M device will need to reset at 60 minutes in order to record 2 hours of topography data. Puff parameters will be recorded using SPA-M devices (puff count, puff duration, puff volume, peak puff flow rate, average puff flow rate, inter puff interval) for each product.

The *ad libitum* product use session on Days 1 through 5 will start at approximately the same time each day, with lunch served at the start of the *ad libitum* product use session, at approximately the same time each day. After completion of the *ad libitum* use session (i.e., approximately 8 hours after the start of the morning controlled product use) on Days 1 to 4, subjects will be allowed to smoke their own cigarettes (*ad libitum*) but will abstain from use of any tobacco- or nicotine-containing products for at least 12 hours prior to the start of morning controlled product use session scheduled on the following day.

The topography device will be monitored to ensure the device is actively recording during each session.

Additional details and instructions for puff topography procedures will be provided separately.

Depending on the availability of topography equipment, puff topography may not be performed for some or all assigned subjects.

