#### Secondary

- 1. To evaluate other pharmacokinetic (PK) parameters of nicotine after the controlled use of each HTP, HHP, or cigarette comparator.
- 2. To evaluate the change in smoking urges observed after the controlled use of each HTP, HHP, or cigarette comparator.
- 3. To evaluate product perception and preference using subjective assessments.
- 4. To evaluate the tolerability and safety of each of the products used.
- 5. To investigate usage behaviour for each product using measurements of topography parameters (puff count, puff duration, puff volume, peak puff flow rate, average puff flow rate, inter puff interval) for each product following *ad libitum* product use sessions.

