On Days 1 through 5, puff topography will be performed over the last 2-hour period during the 4-hour *ad libitum* product use session. The Sodim Smoking Puff Analyzer Mobile (SPA-M) topography device will collect data (puff count, puff duration, puff volume, peak puff flow rate, average puff flow rate, inter-puff interval) for 2 hours. The SPA-M topography device will be reset at 60 minutes in order to collect 2 hours of data.

The *ad libitum* product use session on Days 1 through 5 will start at approximately the same time each day, with lunch served at the start of the *ad libitum* product use session, at approximately the same time each day. After completion of the *ad libitum* use session, subjects will be allowed to smoke their own cigarettes (*ad libitum*) but will abstain from use of any tobacco- or nicotine-containing products for at least 12 hours prior to the start of the morning controlled product use scheduled on the following day.

A new/unused device will be provided to the subjects on each day of HTP/HHP use (i.e., the same device will be used for the morning controlled product use and *ad libitum* product use sessions on the same day).

On Day 5, following completion of study assessments, subjects will be allowed to smoke their own cigarettes and will leave the CRU after completing all final check out requirements.

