Appendix 16.2.5.6 Ad Libitum Smoking (Safety Population)

Subject Number	Study Period	Product	Day	Hour	Start Date	Start Time	Stop Date	Stop Time	Comments
001	Check-in 1	A D	-1 1	-17.75 4.03 6.03 8.05	DDMONYYYY DDMONYYYY DDMONYYYY DDMONYYYY DDMONYYYY	HH:MM:SS HH:MM:SS HH:MM:SS HH:MM:SS	DDMONYYYY DDMONYYYY DDMONYYYY DDMONYYYY DDMONYYYY	HH:MM:SS HH:MM:SS HH:MM:SS HH:MM:SS HH:MM:SS	
	2	В	Ţ	4.03 6.03 8.05	DDMONYYYY DDMONYYYY DDMONYYYY	HH:MM:SS HH:MM:SS HH:MM:SS	DDMONYYYY DDMONYYYY DDMONYYYY	HH:MM:SS HH:MM:SS HH:MM:SS	<this column="" data="" if="" is="" only="" present="" prints=""></this>

<similar to above for all subjects/time points>

Product A: < >
Product B: < >
Product C: < >
Product D: < >
Product E: < >
After Hour 8 in each period, subjects will smoke their OBCC.

Source: SDTM.< >; ADaM.< > Program: /CAXXXXX/sas prg/stsas/lis/programname2022Q1.sas DDMONYYYY HH:MM

			Appe	ndix 16.2.5.7	Prior and (	Concomitant	Medicat	ions (Safe	ty Pop	ulation)		Page 1 of 1
Subject Number 1	Product	Prior?	Medication (WHO DD)	Dosage	Route	Start Date	Start Time	End Date	End Time	Frequency	Indication	Ongoing?
001			None									
002			None									
003		Yes	CETIRIZINE	X MG	BY MOUTH	DDMONYYYY		DDMONYYYY	HH:MM	XXXXXXX	XXXXXXX	No
	В	No	(CETIRIZINE) PARACETAMOL (PARACETAMOL)	X MG	XXXXXXXXX	DDMONYYYY	HH:MM			XXXXXXX	XXXXXXX	Yes

<similar to above for all subjects>

Product A: < >

Product B: < >

Product C: < >

Product D: < >

Product E: < >

Concomitant medications are coded with WHO Drug Dictionary Version 01-Sep-2023 b3.

WHO DD = World Health Organization Drug Dictionary

Prior is defined as a medication administered prior to the first study product administration.

Source: SDTM.< >; ADaM.< > Program: /CAXXXXX/sas prg/stsas/lis/programname2022Q1.sas DDMONYYYY HH:MM

Page 1 of X

Appendix 16.2.5.8 Plasma Nicotine Pharmacokinetic Blood Draw Times and Concentration Data (Safety Population)

Subject.	Study		C	RF	Blood	Draw	Elapsed Time From Last. Product. Use	Unadjusted Concentration	Baseline-Adjusted Concentration	
Number	Period	Product	Day	Hour	Date	Time	(units)	(units)	(units)	Comments
1	1	A	1 < >	-0.05 0.25 0.50	DDMONYYYY DDMONYYYY DDMONYYYY	HH:MM:SS HH:MM:SS HH:MM:SS	0.0 0.265 0.590	X.XX X.XX X.XX X.XX	x.xx x.xx x.xx x.xx	Late Draw

<similar for all other time points and subjects>

Product A: < > Product B: < > Product C: < > Product D: < > Product E: < >

Program: /CAXXXX/sas\_prg/pksas/standardlis/pk\_bld.sas DDMMMYYYY HH:MM
Programmer Notes:

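### SAP 12.5 counts adverse events that start during after-session own-brand smoking, abstinence or follow-up under the period's assigned product, which adds a comparator-cigarette background to every product column

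*SAP*

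**What the plan says.** SAP 12.5 defines emergence with a start but no end: "PUEAE is defined as an AE that is starting or worsening at the time of or after the first study product use". It then assigns each event to a product by onset time: "An AE that occurs between products will be considered product use-emergent to the last product administered prior to onset of the AE".

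The daily schedule leaves a long interval between products. Protocol 6.4.3 puts the end of the ad libitum session at "approximately 8 hours after the start of the morning controlled product use". Protocol 4.3.5 then provides: "On Days -1 through 5, subjects will be allowed to smoke their OBCCs". The SAP shell for the ad libitum smoking listing repeats it: "After Hour 8 in each period, subjects will smoke their OBCC". Before the next controlled session, subjects "will abstain from use of any tobacco- or nicotine-containing products for at least 12 hours". After Day 5 they leave the unit, and a call about 7 days later asks about further events.

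The product table in Protocol 3.1 lists the own-brand cigarette (OBCC) as Product E. SAP 2.1 includes the objective "To evaluate the tolerability and safety of each of the products used", and Protocol 1.3 frames safety as a comparison with OBCC. The AE summary shells have columns for the Product Trial, Products A to E and Overall. None separates evening, overnight or follow-up onsets.

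**The concern.** On a Product A to D day, an event that begins while the subject smokes an own-brand cigarette in the evening is tabulated under the heated tobacco product (HTP) or heated herbal product (HHP), although the cigarette in hand is the comparator. Events from overnight abstinence go the same way. Data collection feeds this window: Protocol 6.4.5.1 schedules an AE inquiry before each product use, so the morning inquiry picks up the previous evening and night.

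The wording is also open to a second reading. Because OBCC is Product E, the last product administered before an evening event on an A to D day could literally be taken to be E. The smoking listing shell keeps the period's assigned product against the Hour 8.05 entry, and the administration-time listings cover only the controlled and ad libitum sessions, so assignment to the day's product is the likelier intent. The SAP does not say so.

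At stake is how far the by-product AE tables describe the products themselves when they are read against the cigarette column.

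**Working it through.** **Inputs.** From the documents: 4 h of PK sampling, then a 4 h ad libitum session; at least 12 h of abstinence; five sequences (ABECD, BCADE, CDBEA, DECAB, EADBC) of 5 subjects; a follow-up call at about 7 days. Assumed: a 24 h cycle between morning sessions (22 to 26 h checked) and all AE risks. The documents give no AE rates, and SAP 4 sets the sample size without statistical considerations.

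**1. Session end.** 4 + 4 = 8 h, which reproduces the figure in Protocol 6.4.3.

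**2. Attribution window.** 24 − 8 = 16 h lie outside the session: 12 h or more of abstinence and at most 24 − 12 − 8 = 4 h of own-brand smoking. The share is 16/24 = 67% (14/22 = 64% to 18/26 = 69%). This is a share of clock time, not of events.

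**3. Balance across products.** Each product falls on Days 1 to 4 in four of the five sequences and on Day 5 in one. That gives 4 × 5 = 20 overnight intervals and 5 follow-up windows per product, E included. Of the 25 × 4 = 100 overnight intervals, 80 follow an HTP or HHP day. The follow-up window is about 7 × 24 − 8 = 160 h. With full completion, each product column covers 25 × 8 = 200 session hours, 20 × 16 = 320 overnight hours and about 5 × 160 = 800 follow-up hours.

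**4. Equal background.** Let p be the in-session risk and b a background risk common to all products. Subject-level incidence is 1 − (1 − p)(1 − b), so the risk difference is the in-session difference times (1 − b). With assumed p of 20% for E and 10% for an HTP or HHP:

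| b | E | HTP/HHP | Ratio | Difference (points) |
|---|---|---|---|---|
| 0 | 20.0% | 10.0% | 0.50 | −10.0 |
| 5% | 24.0% | 14.5% | 0.60 | −9.5 |
| 10% | 28.0% | 19.0% | 0.68 | −9.0 |
| 20% | 36.0% | 28.0% | 0.78 | −8.0 |
| 30% | 44.0% | 37.0% | 0.84 | −7.0 |

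Over b = 5% to 30%, 30% versus 10% takes the ratio from 0.33 to between 0.43 and 0.73, and 12% versus 4% takes it from 0.33 to between 0.54 and 0.85.

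**5. Event counts.** Reading p and b as expected events per subject-period, the difference over 25 subjects is 25 × [(0.10 + b) − (0.20 + b)] = −2.5 for every b.

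**6. Unequal background.** If the background differs, the count difference becomes 25 × [−0.10 + (b_HTP/HHP − b_E)]. An assumed excess of 0.05 after heated-product days gives 25 × (−0.05) = −1.25 in place of −2.5. This is bias, and its direction depends on the sign of the excess.

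**The case against.** The strongest defence is that last-product attribution is a pre-specified, inclusive rule, which is cautious for safety reporting. Restricting attribution to session onsets would move irritation or nausea that starts minutes after four hours of unlimited HTP or HHP use into another category. It would also take own-brand smoking events out of E's column on E days. That stands, and it is why the last-product tables should not be replaced.

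A reader might infer that the rule burdens only the heated products. It does not: E carries the same windows, and the sequences balance them. A reader might also infer that the AE tables are the only safety output by product. They are not. The Aversion score of the Product Evaluation Scale covers dizziness, nausea, too much nicotine and bothersome side effects. It is completed at 240 minutes, before any evening cigarette, and is summarised by product. Device malfunctions are also tabulated by product.

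The plan has partial safeguards too. Investigators grade relationship for each event, Table 14.3.1.3 tabulates it, and the AE listing shows time from last product use. These allow case-by-case inspection, but Tables 14.3.1.1 and 14.3.1.2 count events whatever the grade. In an open-label study, an event during an evening cigarette may be graded differently on an E day than on an A to D day.

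Balanced windows do not guarantee equal background. Evening smoking is limited only by the abstinence rule, and summary Table 14.2.5.2 reports OBCC counts by study period rather than by product, so a difference after HTP or HHP days would not show there.

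**Conclusion.** The point holds as a modest, cheaply corrected weakness in the by-product AE tables. SAP 12.5 places every event starting after Hour 8 under the period's assigned product, and so adds comparator-cigarette and abstinence background to all five columns. With equal background, incidence ratios move towards 1 and subject-level risk differences shrink by (1 − b). With unequal background, the comparison with OBCC is biased.

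A reader might go further and infer that real product differences are hidden in either direction. The documents do not support that: under equal background the expected event-count difference is unchanged, and no difference in background is shown. The AE tables are descriptive and safety is a secondary objective, so no test or error rate is affected.

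The size is unknown because every AE rate used here is assumed. The 16 of 24 h figure rests on a 24 h cycle and does not measure how many events fall outside the session.

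**What to change.** 1. Keep last-product attribution in Tables 14.3.1.1 to 14.3.1.3.
2. State in SAP 12.5 that after-session own-brand smoking does not count as the last product administered on Product A to D days.
3. Add a by-product table of product use-emergent AEs split by onset window: start of controlled use to end of the ad libitum session; evening own-brand smoking and abstinence; follow-up after the Day 5 session. Use the session-onset rows for the comparison of each product with OBCC. Say where events without an onset time are shown, since they cannot be placed in a window.

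The AE onset, session and in-clinic smoking times needed are already planned for collection, so the cost is SAP wording and the programming of one table. The downside is that delayed product effects fall in the later windows; the retained last-product tables cover them.
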